Objectives:	
Primary Objective To investigate pharmacokinetics of single nebulised doses of RPL554 in patients with Cystic Fibrosis (CF)
 
Secondary Objectives
 
• To investigate the bronchodilator effect on peak forced expired volume in 1 second (FEV₁) after single nebulised doses of RPL554 as compared to placebo• To investigate the bronchodilator effect on area under the curve (AUC) FEV₁ over 4, 6 and 8 hours of single nebulised doses of RPL554, as compared to placebo• To assess the tolerability and safety of single nebulised doses of RPL554 in patients with CF 
Exploratory Objectives
 
• To examine the anti-inflammatory effects of single nebulised doses of RPL554 in patients with CF	
Study Design and Methodology:	
This is a Phase IIa, randomised, double blind, placebo controlled, complete block three way crossover study to investigate the pharmacokinetics of nebulised RPL554 (1.5 mg and 6 mg) in adult patients with CF. It is planned to enrol sufficient patients to ensure that 10 complete all three treatment periods at two centres. The study comprises five visits: screening (Visit 1), three treatment visits (Visit 2 to Visit 4) and an end of study visit (Visit 5). Patients will be screened for eligibility (Visit 1), including a reversibility test with salbutamol, between 3 and 14 days prior to the first dose of study treatment.
 
Eligible patients will then attend for three separate 1 day treatment visits (Visits 2 to Visit 4) each separated by at least a 3 day washout period. Patients will be randomised pre-dose at Visit 2. Patients will receive a single nebulised dose of 1.5 mg RPL554 or 6 mg RPL554 or placebo at each visit. The pre-dose FEV₁ at Visit 3 and Visit 4 must be within $\pm 20\%$ of the pre-dose FEV₁ at Visit 2 in order to ensure consistent baseline FEV₁ for each study treatment. At each visit, patients will be resident at the study centre from the morning until at least 8 hours after dosing. Patients will be discharged after 8 hours, but return the following morning for final assessments 24 hours after dosing.
 
The following will be performed at each treatment visit:
 
• Measurements of lung function (FEV₁ and forced vital capacity [FVC]) pre-dose and up to 24 hours post-dose• Blood sampling pre-dose and up to 24 hours post-dose for pharmacokinetic analysis	

	
 • Sputum sampling pre-dose and at 8 and 24 hours post-dose for rheology and measurement of inflammatory mediators (interleukin 8 [IL-8], tumour necrosis factor alpha [TNF-α], myeloperoxidase [MPO]) • Exhaled breath pH measurement pre-dose and at 8 and 24 hours post-dose (at UK centre only) • Urine pregnancy test pre-dose (female patients only) • Vital signs and 12-lead electrocardiogram (ECG)s pre-dose and up to 8 hours post-dose 
An end of study visit (Visit 5) will be performed 3 to 10 days after the last dose of study treatment. Adverse events will be recorded throughout the study and laboratory safety tests, a physical examination and urine pregnancy tests (female patients only) will be performed at screening (Visit 1) and at the end of study visit (Visit 5).

Number of Patients Planned:	10 patients must complete all three treatment visits (Visit 2 to Visit 4) up to the 24 hour assessments in the study. Any patients who do not complete will be replaced.
Main Criteria for Eligibility:	
Inclusion Criteria
 
 1. Sign an informed consent document indicating they understand the purpose of and procedures required for the study and are willing to participate in the study. 2. Male or female aged ≥ 18 years old, at the time of informed consent. Females of childbearing potential must have been using a consistent and reliable form of contraception from the last menses before the first study treatment administration, and must commit to continue to do so during the study and for 3 months after the last dose of study treatment. 3. Have a 12-lead ECG recording at screening (Visit 1) and Visit 2 pre-dose showing the following: 
 • Heart rate between 50 and 100 beats per minute • QT interval corrected for heart rate using Fridericia's formula (QTcF) interval ≤ 450 msec • QRS interval ≤ 120 msec • PR interval ≤ 200 msec • No clinically significant abnormality including morphology (e.g. left bundle branch block, atrioventricular nodal dysfunction, ST segment abnormalities) 4. Capable of complying with all study restrictions and procedures including ability to use the study nebuliser correctly. 5. Body mass index between 18 and 30 kg/m^2 (inclusive) with a minimum weight of 40 kg. 6. Patients with a genetic diagnosis of CF. 7. Spirometry demonstrating an FEV₁ of $\geq 40\%$ and $\leq 80\%$ of predicted normal. 8. Capable of withdrawing from long acting bronchodilators for 48 hours prior to study visits, and short acting bronchodilators for 8 hours prior to study visits. 9. Clinically stable CF in the 2 weeks prior to randomisation (Visit 2). 
Exclusion Criteria
 
 1. History of cirrhotic liver disease or portal hypertension. 2. CF exacerbation requiring hospitalisation in the month prior to screening (Visit 1) or prior to randomisation (Visit 2). 3. Use of oral or intravenous antibiotics (in addition to usual maintenance therapy) in the 2 weeks prior to screening (Visit 1) or randomisation (Visit 2). 4. Other non-CF-related respiratory disorders: Patients with a current diagnosis of active tuberculosis, lung cancer, sarcoidosis, sleep apnoea, known alpha-1 antitrypsin deficiency or other active pulmonary diseases. 5. Previous lung resection or lung transplant.

[figure not shown]
	
6. History of, or reason to believe a patient has, drug or alcohol abuse within the past 3 years.7. Received an experimental drug within 3 months or five half-lives, whichever is longer.8. Patients with a history of chronic uncontrolled disease, unless CF related, including, but not limited to, cardiovascular (including arrhythmias), endocrine, active hyperthyroidism, neurological, hepatic, gastrointestinal, renal, haematological, urological, immunological or ophthalmic diseases that the Investigator believes are clinically significant.9. Documented cardiovascular disease: angina, recent or suspected myocardial infarction, congestive heart failure, a history of unstable, or uncontrolled hypertension, or has been diagnosed with hypertension in last 3 months.10. Has had major surgery, (requiring general anaesthesia) in the 6 weeks prior to screening (Visit 1), or will not have fully recovered from surgery, or planned surgery through the end of the study.11. Infection with nontuberculous mycobacteria, methicillin-resistant Staphylococcus aureus (MRSA) or Burkholderia species.12. Use of immune-suppression; long term use of prednisolone >10 mg/day.13. History of malignancy of any organ system within 5 years with the exception of localised skin cancers (basal or squamous cell).14. Clinically significant abnormal values for safety laboratory tests (haematology, biochemistry or urinalysis) at screening (Visit 1), as determined by the Investigator.15. A disclosed history or one known to the Investigator, of significant non-compliance in previous investigational studies or with prescribed medications.16. Patients treated with ivacaftor or ivacaftor/lumacaftor will be excluded.17. Requires oxygen therapy on a regular basis.18. Pregnancy or lactation (female subjects only).19. Any other reason that the Investigator considers makes the patient unsuitable to participate.
Study Treatments:	Patients will receive the following three single doses of study treatment, one at each treatment visit (Visit 2 to Visit 4), in a randomised sequence: 1.5 mg RPL554, 6mg RPL554 or placebo. All study treatments will be administered using the inhaled route using a standard Jet nebuliser (PARI LC Sprint plus a PARI TurboBOY SX compressor unit). 
Duration of Treatment:	The approximate planned duration for each patient will be up to 52 days: 3 to 14 days screening, up to 28 days treatment (three treatment visits each usually separated by 3 to 14 days) and an end of study visit 3 to 10 days after the last treatment visit.
Statistical Methods:	
This is a sample size of convenience. No powering calculation was performed.
 
Pharmacodynamics:
 
Treatments will be compared using analysis of covariance adjusting for treatment, period, patient and baseline. Multiplicative models will be used for FEV₁ and additive models for blood pressure, pulse rate and ECG heart rate. Active treatments will first be compared to placebo using a closed test procedure (within substance) starting with the highest dose.
 
Other Analyses:
 
Biomarker measurements and exhaled breath pH will be analysed by Student's T test. Other data will be analysed descriptively. Adverse events will be presented by system organ class and preferred term and summarised by study treatment and further by intensity and relationship to study treatment.

TABLE OF CONTENTS AND LIST OF TABLES AND FIGURES

Table of Contents

SPONSOR SIGNATURE PAGE	2
INVESTIGATOR SIGNATURE PAGE	3
CONFIDENTIALITY STATEMENT	3
CONTACT LIST	4
DETAIL OF AMENDMENTS SINCE THE PREVIOUS VERSION.....	6
SYNOPSIS.....	7
TABLE OF CONTENTS AND LIST OF TABLES AND FIGURES	10
Table of Contents	10
List of Tables and Figures	13
LIST OF ABBREVIATIONS AND DEFINITION OF TERMS	14
1 INTRODUCTION	16
1.1 Disease and Study Treatment Review	16
1.2 Summary of Risks and Benefits.....	18
2 OBJECTIVES.....	19
2.1 Primary Objective	19
2.2 Secondary Objectives.....	19
2.3 Exploratory Objectives	19
3 INVESTIGATIONAL PLAN	20
3.1 Overall Study Design and Plan Description	20
3.2 Discussion of Study Design, including the Choice of Control Groups	21
3.3 Planned Duration of the Study	22
3.4 Definition of the End of the Study.....	22
4 SELECTION OF STUDY POPULATION.....	22
4.1 Inclusion Criteria.....	22
4.2 Exclusion Criteria	23
4.3 Removal of Patients from Therapy or Assessment.....	23
4.3.1 Study Treatment Discontinuation	24
4.3.2 Patient Withdrawal	24
4.3.3 Study Discontinuation.....	24
4.3.4 Replacement Policy	25
5 STUDY TREATMENTS	25
5.1 Study Treatments Administered.....	25
5.2 Identity of Study Treatments.....	25
5.3 Preparation and Labelling	26
5.4 Selection of Doses, Dosing Schedule and Route of Administration.....	26
5.4.1 Selection of Doses in the Study	26

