1.2 Summary of Risks and Benefits

Data from non-clinical studies suggest a potential for hypotension and tachycardia. However, RPL554 has been administered to about 249 subjects in clinical studies to date and has been well tolerated in COPD patients, healthy subjects, asthmatics and allergic rhinitis. No serious adverse events (SAEs) during scheduled treatment and follow-up have been reported with RPL554.

Adverse events that have been reported at least twice in subjects who have received single or multiple doses of the solution formulation of RPL554 were general mild and in descending order of frequency are headache, nasal congestion, dizziness, somnolence, rhinorrhoea, fatigue, larynx irritation, vasodilation, asthma, dry throat, respiratory tract infection, and sneezing. Many of the events also occurred with a similar frequency with placebo. The only other observation noted was a modest increase in standing heart rate in one study.

The suspension formulation of RPL554 is pH balanced, and has favourable non-clinical toxicology and pharmacokinetic data. The pharmacokinetics with the suspension formulation is dramatically different from that with the solution formulation. The absorption is much slower, with a T_{max} of 1 to 1.5 hours, and the terminal half-life much longer (8 to 13 hours). The C_{max} is lower than with the solution formulation, although the total exposure is greater.

There has been no evidence of significant adverse events related to the cardiovascular or gastrointestinal systems, except associated with an increase in heart rate at high doses (12 mg to 24 mg). These small increases in heart rate may relate to the PDE3 inhibitory activity of the compound. In single dose studies there appears to be an increase in the rate of headache, which is most pronounced at doses over 6 mg. There was no other apparent dose related adverse events, with the exception of palpitations in patients dosed at 24 mg. Results from multiple dose data in patients with COPD suggests a transient increase in dizziness; the majority of which occurred during spirometry or dosing, but otherwise the rate of adverse events were similar in RPL554 or placebo treated patients. There was an apparent increase in mild adverse events in healthy subjects treated with high doses of RPL554, which may be associated with the higher serum levels in healthy individuals than in those with obstructive lung disease.

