10.4.5 Pharmacodynamics

For FEV_1 the average effect, (E_{av}), will be calculated as the AUC divided by the length of the time interval of interest. In addition the peak effect on FEV_1 during these time intervals will be computed as the maximum value (E_{max}).

Computed pharmacodynamic parameters for FEV_1 will be compared between placebo and the two doses of RPL554 using analysis of covariance (ANCOVA) models with fixed factors for treatment, period and patient, and using the baseline of the day as a covariate. FEV_1 will be analysed using multiplicative models, which means that data is logged prior to analysis and the result then transformed back to the linear scale giving treatment differences as ratios of geometric means.

Results of the comparisons will be expressed as the mean geometric ratio with 95% confidence intervals and associated, 2-sided, p-value.

All hypothesis testing was done using two-sided alternative hypotheses. P-values less than 5% will be considered statistically significant.

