6.4.7.3 Vital Signs

Vital signs data will be summarised by treatment group and time point. The change from baseline (pre-dose at each treatment visit) to each post-dose time point will also be calculated and summarised. Data will further be illustrated by shift tables (showing changes from low/normal/high) and shift plots for the change from baseline to worst case during the treatment period.

The baseline value will be defined as the last scheduled, unscheduled or repeat value collected prior to dosing in a period. The tabulation will only include scheduled visits; all unscheduled assessments will be displayed in the listing as appropriate.

Vital signs will be listed showing reference ranges and flagging all abnormal findings and their clinical significance (CS or NCS). Out of reference range values will be flagged as high (H) or low (L). A similar listing including all post-dose vital signs values found abnormal, including the baseline result and clinical significance, will also be produced.

Further, for data collected during treatment days, graphics will include individual and mean value curves over time for each variable expressed as change from baseline.

6.4.7.4 12-Lead ECG

12-lead ECG data will be summarised and illustrated in the same way as vital signs data. In addition, for QTcF, a plot showing the baseline value of the treatment day on the x-axis versus the post-dose value indicating the largest absolute change on the y-axis will be constructed. QTcF data will also be summarised according to frequencies of values >450 ms, >480 ms and >500 ms and according to frequencies of shifts from baseline of the treatment day to post-dose of >30 ms and >60 ms.

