6.6 Statistical Issues

All hypothesis testing will be done using two-sided alternative hypotheses. P-values less than 5% will be considered statistically significant.

No adjustment for multiple testing will be done. A closed testing procedure will be applied: first the higher dose of RPL544 will be tested versus placebo and then, if statistically significant, the lower dose of RPL554 versus placebo. Finally the two doses of RPL554 will be compared.

Patients withdrawn after only one treatment period will not be included in the efficacy analyses. No imputation of missing data other than described under Section 6.4 will be performed.

Sensitivity analyses of pharmacodynamic data will be done to explore the impact of outliers or, for FEV₁ parameters, the use of rescue medication during the clinic visits.

All available data from all patients who have received study treatment will be listed and summarised. Any unscheduled or unplanned readings will be presented within the patient listings, but only the scheduled readings will be used in any summaries. If a visit is rescheduled due to variability in FEV₁ or other reason, the rescheduled visit will be listed and summarised as the valid visit.

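### Synopsis and SAP disagree on how blood pressure, pulse rate and ECG heart rate are compared with placebo, and neither plans an ungated dose-minus-placebo estimate with a confidence interval

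*Protocol*

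**What the plan says.** **Protocol synopsis, Statistical Methods.** Under Pharmacodynamics, treatments are compared by analysis of covariance with treatment, period, patient and baseline. FEV1 gets multiplicative models. The same sentence adds "additive models for blood pressure, pulse rate and ECG heart rate". The next sentence reads: "Active treatments will first be compared to placebo using a closed test procedure (within substance) starting with the highest dose". The statement that other data are handled descriptively comes later, under a separate label.

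**Protocol body.** Section 10.4.5 specifies the covariance model for FEV1 only and does not mention the closed test. Section 10.4.7 summarises vital signs and ECG by treatment and time point, with change from the pre-dose value of the day.

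**SAP.** Section 6.4.7.3 says "Vital signs data will be summarised by treatment group and time point", with change from baseline, shift tables and plots. Section 6.4.7.4 treats ECG the same way and adds QTcF threshold counts. Section 6.6 states the gate in general terms, 6 mg against placebo "and then, if statistically significant, the lower dose of RPL554 versus placebo", and names no variables. Section 6.8, on changes to planned analyses, covers only the pharmacokinetic parameters.

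**Risk named.** Protocol 1.2: "Data from non-clinical studies suggest a potential for hypotension and tachycardia". It also reports small clinical heart-rate increases at 12 to 24 mg. Both documents list heart rate, blood pressure and pulse among the safety endpoints.

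**The concern.** A hierarchical gate protects against false claims of benefit. Applied to harm it works the wrong way: a non-significant 6 mg result would remove the formal statement on 1.5 mg, and in a study this small non-significance says little. The synopsis wording allows that reading, and SAP 6.6 does not exclude it.

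If the SAP's safety sections govern instead, the gate has nothing to act on, but the comparison with placebo goes too. The reader gets three columns of means and changes, and must judge the placebo-corrected change, and its uncertainty, by eye. The study is a placebo-controlled crossover in which each patient is his or her own control, so the within-patient difference is the most informative safety contrast it can provide. For FEV1 the SAP reports all three contrasts with 95% intervals; for the haemodynamic variables it reports none.

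**Working it through.** **1. What each place provides for blood pressure, pulse rate and ECG heart rate**

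| Place | Model against placebo | Gate | Interval for dose minus placebo |
|---|---|---|---|
| Protocol synopsis | Yes, additive | Yes, as worded | Not stated |
| Protocol 10.4.5 | No (FEV1 only) | Not mentioned | No |
| Protocol 10.4.7 | No, descriptive | No | No |
| SAP 6.4.7.3, 6.4.7.4 | No, descriptive | No | No |
| SAP 6.6 | None specified | Yes, variables unnamed | No |
| SAP 8.1 table list | Statistical-analysis tables only for FEV1, sputum measures and breath pH | Not stated | No |
| SAP 6.8 | Removal of the synopsis models not recorded | Not stated | Not stated |

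**2. What the missing interval would look like**

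The plan has no figure to reproduce, because the sample size is one of convenience.

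Inputs from the documents: 10 completers, three periods, and factors treatment, period and patient with baseline as covariate. Tests are two-sided ("All hypothesis testing will be done using two-sided alternative hypotheses") and "P-values less than 5% will be considered statistically significant". The within-patient SD, s, is not given; 4 to 8 bpm is assumed for illustration. One summary value per patient and period is assumed.

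- Residual degrees of freedom: 30 − 1 − 9 (patients) − 2 (periods) − 2 (treatments) − 1 (baseline) = 15.
- Standard error of a dose-minus-placebo difference: s × √(2/10) = 0.447 s. This ignores any loss from period imbalance or from the covariate, so it is slightly optimistic.
- t(0.975, 15) = 2.131. Half-width of the 95% interval: 2.131 × 0.447 s = 0.953 s.
- If a difference just misses significance, the observed value is just under 0.953 s and the upper limit is just under 2 × 0.953 s = 1.906 s.
- True difference needed for 80% power (non-central t): 1.34 s.

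| Assumed s (bpm) | Half-width | Upper limit if just non-significant | Difference for 80% power |
|---|---|---|---|
| 4 | 3.8 | 7.6 | 5.4 |
| 6 | 5.7 | 11.4 | 8.0 |
| 8 | 7.6 | 15.3 | 10.7 |

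If the synopsis test were run and the true rise at 6 mg were 5 bpm (also an assumption), it would be non-significant with probability 26%, 59% and 74% at s = 4, 6 and 8. A p-value of 0.05 or more is therefore weak evidence of no effect, while the interval shows directly what remains compatible with the data.

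**The case against.** The strongest reply is that the operative plan contains no test of these variables. Protocol 10.1 leaves the detail to the SAP, and the SAP plans no p-value for heart rate or blood pressure. A gate with no test behind it suppresses nothing. Every treatment, 1.5 mg included, is summarised at every time point with shift tables, curves, flagged abnormal values and QTcF counts. Where the SAP does model, for FEV1, it states all three contrasts with intervals, so even there the gate limits claims and not estimates. Descriptive safety analysis is a normal choice in an unpowered study with a pharmacokinetic primary endpoint, and the clinical heart-rate signal in Protocol 1.2 was at doses above both used here.

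Most of this stands, and it rules out three stronger readings:

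- A reader might infer that the 1.5 mg safety comparison is closed off. It is not: the descriptive summaries do not depend on the 6 mg result.
- A reader might infer that a statement of no significant effect on heart rate will be issued. The SAP plans no test that would produce one.
- A reader might put a figure on the chance of missing a 1.5 mg effect because of the gate. That needs an assumed SD and an assumed effect at both doses. Setting the two effects equal sits badly with the roughly dose-proportional exposure reported in Protocol 1.1.

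The reply does not remove the mismatch. The synopsis still promises models and a gate, SAP 6.6 does not limit its scope, SAP 6.8 is silent, and no interval is planned under either reading.

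**Conclusion.** The point holds as a minor one. The documents give either a gated comparison (synopsis) or no placebo-corrected estimate (Protocol 10.4.7 and the SAP) for the haemodynamic risks that the protocol names. Nothing in the 1.5 mg safety data is lost; what is missing is an ungated estimate with its uncertainty.

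The half-width of about 0.95 within-patient SDs follows from 10 completers and the synopsis model. The values in bpm rest on the assumed SD of 4 to 8 bpm, and the probabilities of a non-significant result also rest on an assumed 5 bpm effect. The severity is low because the study is unpowered and its primary endpoint is pharmacokinetic.

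**What to change.** 1. In the synopsis and SAP 6.6, say that the closed test applies to the FEV1 parameters only. Bring the synopsis, Protocol 10.4.7 and SAP 6.4.7 into line on the haemodynamic variables, and record the change in SAP 6.8.
2. In SAP 6.4.7.3 and 6.4.7.4, and in the table list, add one table: each dose minus placebo for blood pressure, pulse rate and ECG heart rate, from an additive model with treatment, period, patient and baseline of the day, with 95% confidence intervals. Report both doses regardless of significance. Name in advance the summary or time points modelled, since the synopsis does not.
3. State that the reading rests on the interval, and that p ≥ 0.05 is not evidence of no effect.

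The cost is some wording and one table, from data already collected and a model the synopsis already names. The drawback is that intervals will be wide and some may exclude zero by chance, so the table should be labelled descriptive.
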